# Parexel International

Suzhou Connect Biopharmaceuticals Ltd.

CBP-201-WW003

## Statistical Analysis Plan

- s. Injection site reactions should be assessed at all visits from the first dosing day until the end of the study. The previous injection site(s) should be assessed prior to dosing. On all dosing days, the new injection site should be assessed prior to the patient's release. The SC injection site may be assessed using a standard instrument provided in Appendix or described as needed by the Investigator in the medical notes. Clinically significant findings as determined by the Investigator will be reported as an AE. See section 8.6 for more details.
- t. Unscheduled visits may be conducted as needed, and additional assessments performed at these visits are at the discretion of the Investigator.
- u. CT scan will only be required for subjects that are enrolled at Study Sites that are approved and qualified to perform CT Scans.

---

TP-GDO-WW-016-08

Effective Date: 26 Nov 19

Related to: SOP-GDO-WW-019

**CONFIDENTIAL**

**Project Document Version No. 2.0**

**Project Document Effective Date:** Date of last signature

Page 15 of 52

### 3.3 Endpoints

#### 3.3.1 Efficacy Endpoints

There will be two co-primary endpoints:

- Change from baseline at Week 24 in endoscopic NPS
  - Endoscopic NPS score is graded based on polyp size (recorded as the sum of the right and left nostril scores with a range of 0 to 8; higher scores indicate worse status)
- Change from baseline at Week 24 in average daily nasal congestion score (NCS)

#### 3.3.1.2 Secondary Efficacy Endpoints

- Change from baseline at Week 24 in:
  - Percentage of maxillary sinus volume occupied by disease on CT and Lund-Mackay Computed Tomography scores from patients enrolled at Study Centers that are approved and qualified to perform CT scans
  - University of Pennsylvania Smell Identification Test (UPSIT)
  - Visual Analogue Scale for Rhinosinusitis (VAS-RS)
  - Total Nasal Symptom Score (TNSS)
  - 22-item Sinonasal Outcome Test (SNOT-22)
  - Average daily anterior rhinorrhea score (from diary)
  - Average daily posterior rhinorrhea score (from diary)
  - Average daily loss of smell score (from diary)
  - Daily subject-assessed Nasal Peak Inspiratory Flow (NPIF)
- Requirement of rescue treatment (systemic corticosteroid for > 5 consecutive days) or having had surgery for nasal polyps through Week 24
- Time to rescue treatment (systemic corticosteroid for > 5 consecutive days) or surgery for nasal polyps through Week 24

#### 3.3.1.3 Exploratory Efficacy Endpoints

- Change from baseline at Week 24 in Forced Expiratory Volume in 1 second (FEV1) for patients with asthma
- Proportion of patients with minimal clinically important difference  $\geq 8.9$  in SNOT-22 at Week 24
- Change from baseline at Week 16 in endoscopic NPS
- Change from baseline at Week 16 in average daily NCS
- Change from baseline at Week 24 in European Quality of Life Scale (EQ-5D-5L)
- Healthcare resource utilization through Week 24

### 3.3.1.4 Pharmacodynamic Endpoints

- Change from Baseline in blood levels of IgE
- Change from Baseline in peripheral eosinophil counts
- Change from Baseline in other markers of atopic inflammation in the blood [eosinophil cationic protein (ECP), thymus and activation-regulated chemokine (TARC), Eotaxin-3, and periostin.]

### 3.3.1.5 Pharmacokinetic Endpoints

Whole blood for plasma CBP-201 concentrations will be obtained and analyzed. The individual steady-state trough PK profile will be calculated for each treatment schedule.

Additional sampling will be obtained after the last treatment dose as noted above to characterize the return to baseline.

The details of PK analysis will be reported in a separate PK analysis plan.

### 3.3.1.6 Safety Endpoints

- Adverse events (AEs) reported, including serious adverse events (SAEs) and adverse events of special interest (AESI)
- Vital signs (body temperature, respiratory rate, blood pressure, and heart rate)
- Physical examinations
  - Complete: general appearance, skin, eyes/ears/nose/throat, thyroid, head and neck, cardiovascular system, respiratory system, abdomen, fundoscopy (optional), extremities, lymph nodes, musculoskeletal, and nervous system
  - Brief: general appearance, eyes, lungs, lymph nodes
- 12-lead electrocardiogram (ECG) parameters
- Injection site evaluations
- Safety laboratory parameters (urinalysis, serum chemistry, and hematology)
- Antidrug antibodies (ADA) and neutralizing antibodies (NAb)

## 4 STATISTICAL METHODS

### 4.1 Data Quality Assurance

All tables, listings, and figures to be included in the report will be independently checked by biostatistician for consistency, integrity and in accordance with standard Parexel procedures.

### 4.2 Definitions

#### Age at Baseline

Age will be calculated using the date of birth and date of the baseline visit as below:

Integer part of [(Date of Baseline Visit – Date of Birth) / 365.25]

Baseline

Unless otherwise specified, baseline is defined as the last non-missing value prior to the first dose of study drug. If time is not collected but the assessment is performed on the same day as the first dose of study drug, it would be considered as baseline.

Baseline Week

For weekly average analysis, baseline week is defined as 7 days prior to the baseline visit (Study day ranges from -7 to -1).

Change from Baseline

Change from baseline is defined as post-baseline value minus baseline value.

Study Day 1

Study day 1 is defined as the date of randomization for untreated randomized subjects or the date of first dose for treated subjects.

Study Day

Study Day will be calculated relative to the date of randomization for untreated randomized subjects and relative to the date of first dose for treated subjects.

If event is prior to the first dose, then study day is calculated as:

$$\text{Date of Event} - \text{Date of First Dose}$$

If event is after the first dose, then study day is calculated as:

$$\text{Date of Event} - \text{Date of First Dose} + 1$$

Duration of Treatment

Duration of Treatment (days) will be calculated as:

$$\text{Last Date of Dose} - \text{First Date of Dose} + 1$$

Treatment-Emergent Adverse Events

Treatment-emergent adverse events are defined as any adverse events occurred or worsen during the treatment-period, whether considered related to the treatment.

Where the AE start date is missing, adverse events will be assumed to be treatment-emergent, unless there is clear evidence (through comparison of partial dates) to suggest that the adverse event started prior to the first dose of study treatment.

Prior and Concomitant Medication

Prior and concomitant medication is defined as any medications that started before the first dose of study drug and stops on or after the first dose of study drug.

Prior Medication

Prior medication is defined as any medications that started and stopped before the first dose of study drug.

Concomitant Medication

Concomitant medication is defined as any medications that started on or after the first dose of study drug.

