6.15 Visit 15 (End of Treatment) (Study Day 169 ± 3 days/Week 24)

The following assessments and procedures should be completed in the order given below, if possible:

- Review and record changes in of concomitant medications
- Vital sign measurements
- Brief physical exam
- Review of patient diary and NPIF data
- Record body weight
- CT scan (only required for subjects that are enrolled at Study Sites that are approved and qualified to perform CT Scans)
- NCS assessment

Suzhou Connect Biopharmaceuticals, Ltd

Protocol CBP-201-WW003

Investigational Drug: CBP-201

21 December 2021

- EQ-5D-5L assessment
- VAS-rhinosinusitis assessment
- SNOT-22 assessment
- TNSS assessment
- UPSIT assessment of smell
- Nasal endoscopy and NPS scoring
- Pulmonary Function Tests (Spirometry) for patients with comorbid asthma only
- Healthcare resource utilization questionnaire
- 12-lead ECG
- Urine pregnancy test
- Safety laboratory samples (hematology, serum chemistry, urinalysis)
- PK blood sample (predose)
- PD blood sample (predose)
- ADA blood sample (predose)
- Administer study drug
- Injection site assessment
- Dispense optional take-home rescue medications (albuterol/salbutamol) to patients with asthma, if needed. Remind patients to document the use in their patient diary.
- AE review and recording

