6.16 Visit 16 (Study Day 197 ± 5 days/Week 28)

The following assessments and procedures should be completed in the order given below, if possible:

- Review and record changes in concomitant medications
- Vital sign measurements
- Brief physical examination
- Review patient diary and NPIF data
- Hematology and serum chemistry tests
- PK sample

- Injection site assessment (previous injection)
- Urine pregnancy test
- Dispense optional take-home rescue medications (albuterol/salbutamol) to patients with asthma, if needed. Remind patients to document the use in their patient diary.
- AE review and recording

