8.3 Adverse Event Reporting

Both AEs and SAEs will be recorded from the time the patient signs the ICF until Visit 17 or Early Termination Visit, whichever occurs first. All AEs must be fully recorded into the source documents throughout the entire study period and will be transcribed into the AE eCRF, whether or not they are considered to be drug related.

If a diagnosis could be established, record the diagnosis as AE; If impossible to establish a diagnosis, record Signs and symptoms as AEs until a diagnosis could finally be determined, information including signs and symptoms of each AE should be described in detail, including

- Onset time and date
- Offset time and date
- Severity (mild, moderate, severe, life-threatening, death)
- Relationship to study drug (related, not related),
- Action taken with study drug (dose not changed, study drug interrupted, study drug withdrawn, not applicable, unknown)
- Outcome (recovered/resolved, recovering/resolving, not recovered/not resolved, resolved with sequelae, fatal, unknown)

Adverse events should be followed until the event is resolved and/or stabilized whether or not the event is considered related to study drug. Adverse events resulting from concurrent illnesses, reactions to concurrent illnesses, reactions to concurrent medications, or progression of disease states must also be reported. All AEs will be followed to adequate resolution. Medical Dictionary for Regulatory Activities (MedDRA) will be used to code AEs and medical history. In addition, the World Health Organization Drug Dictionary (WHODrug) will be used to code medication usage.

Any medical condition that is present at the time the patient is screened but does not deteriorate should not be reported as an AE. However, if it deteriorates at any time during the study, it should be recorded as an AE.

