9.6 Safety Data Analysis

Adverse events will be coded using the MedDRA. Treatment-emergent adverse events (TEAEs) are defined as any AEs occurred or worsen during the treatment period from first administration of study treatment to end of the follow-up period, whether or not considered related to the treatment. The incidence of TEAEs will be presented overall, by system organ class (SOC), and by preferred term for each treatment group. Incidence of AEs by severity and relationship to study drug will also be presented for each treatment group. Deaths, SAEs, AESIs and adverse events resulting in discontinuation from the study will be summarized by treatment group.

Safety laboratory parameters, ADA and NAb, vital signs, ECG parameters will be summarized by treatment group and by scheduled visit. Change from Baseline in these continuous parameters will also be summarized by treatment group and by scheduled visit.

For AESI, the percentage of subjects with incident AE, the risk difference, its 95% confidence interval, and p-value will be provided. The confidence intervals and p-values are not adjusted for multiplicity and therefore must be considered accordingly. The requirement will be at least 4 subjects in any treatment arm. The cut-off of at least 4 events was chosen because the 95% confidence interval for the between-group difference in percent incidence will always include zero when treatment groups of equal size each have less than 4 events and so adds little to the interpretation of potentially meaningful differences.

Two approaches will be used for handling safety data occurring after the initiation of rescue therapy. The first approach will exclude all data following the initiation of rescue, in order to avoid the confounding influence of the rescue therapy. The second approach will include data following the initiation of rescue therapy. For the overall study analyses, the “including rescue” approach will be considered primary for all safety endpoints.

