### 3 INVESTIGATIONAL PLAN

#### 3.1 Overall Study Design and Plan

This is a multicenter, randomized, double-blind, placebo-controlled study evaluating the effect of CBP-201 in patients with CRSwNP whose disease remains inadequately controlled despite daily treatment with INCS therapy.

The study consists of three periods:

- Screening/Run-In Period: 4 weeks
- Treatment Period: CBP-201/Placebo for 24 weeks
- Post-Treatment Follow-Up Period: 8 weeks

It is anticipated that approximately 147 male and female patients with chronic rhinosinusitis with large bilateral nasal polyps that remain uncontrolled despite daily treatment with INCS will be recruited into the study. Approximately 50% of the randomized patients will be targeted to have comorbid asthma, defined as  $\geq 12\%$  reversibility (improvement in FEV1) and use of ICS < 1000  $\mu\text{g}/\text{day}$ , and treatment will be stratified on a presence of comorbid asthma.

CBP-201 will be provided as a single use 2 mL vial containing 1.2 mL clear to slightly yellow sterile solution of CBP-201 targeted to be approximately 150 mg/mL. Placebo will be provided as a single use 2 mL vial containing 1.2 mL solution of identical excipients without CBP-201. Similar volumes and number of vials are to be used for placebo doses.

After screening/run-in has been complete, eligible patients will be stratified by presence of comorbid asthma and randomized 1:1:1 to the following treatments:

- CBP 201 300 mg SC every 2 weeks with a 600 mg loading dose on Day 1
- CBP 201 300 mg SC every 4 weeks with a 600 mg loading dose on Day 1. This group will also receive volume matched placebo every 4 weeks on alternate visits to maintain the blind
- Placebo volume-matched SC dosing every 2 weeks with a placebo loading dose on Day 1

Dosing will be volume matched to maintain double-blind with 4 times 1 mL injections on Day 1 and 2 times 1 mL injections on subsequent dosing days.

A detailed schedule of assessments for the study is provided in [3.2](#).

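### SAP 4.2 drops the protocol's end point for treatment-emergent adverse events, so on a literal reading events that start in the 8-week follow-up miss the TEAE and AESI tables

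*SAP*

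**What the plan says.** Protocol 9.6 defines TEAEs as "any AEs occurred or worsen during the treatment period from first administration of study treatment to end of the follow-up period", whether or not they are considered related to treatment. SAP 4.2 (Definitions) has: "Treatment-emergent adverse events are defined as any adverse events occurred or worsen during the treatment-period, whether considered related to the treatment". The start point, the end point and the words *or not* are gone.

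SAP 3.1 lists the study periods separately: "Treatment Period: CBP-201/Placebo for 24 weeks" and "Post-Treatment Follow-Up Period: 8 weeks". The SAP's schedule of assessments also has separate column headings for the two. SAP 4.11.4 uses the 24-week treatment period as a cut-off for the rescue and surgery analysis and does not count later events.

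Protocol 6.15 lists "Administer study drug" at Visit 15 (Week 24, nominal Day 169). Protocol 8.3 states the collection window: "Both AEs and SAEs will be recorded from the time the patient signs the ICF until Visit 17 or Early Termination Visit", whichever occurs first. Visit 17 is nominal Day 225.

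SAP 4.12.3 defines AESIs as TEAEs. It gives risk differences, confidence intervals and p-values against placebo only if at least 4 subjects in some arm have the event.

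SAP 4.15 records the early termination, the shift of the planned analyses towards safety, and the reduced efficacy analyses. It does not mention the TEAE window.

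**The concern.** The TEAE flag decides which events enter most of the safety output. If a programmer takes the treatment period to be the 24 weeks of SAP 3.1, an event that starts in follow-up is collected and listed but not counted as treatment-emergent. It then drops out of the system organ class and preferred term tables by severity, grade 3 or higher and relatedness. It also drops out of the AESI incidence tables and the only between-arm AESI comparisons.

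Follow-up begins immediately after a dosing visit. The Day 169 injection site is checked before the patient leaves, but its next scheduled check is at Week 28, inside follow-up.

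Safety is what this report will now mainly present. A reader of the TEAE tables would assume the protocol's window and could not see from the tables that a shorter one had been used.

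**Working it through.** **Inputs.** End of Treatment visit: Day 169 ± 3 (protocol 6.15). End of Study visit: Day 225 ± 5 (protocol 6.17). Week 24 safety analysis window: Days 166 to 172 (SAP Table 1). Dosing visits: V2 and V4 to V15 (schedule of assessments).

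**The plan's own figure.** Follow-up length = 225 − 169 = 56 days; 56 / 7 = 8 weeks, which matches the stated 8 weeks.

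**Days outside the literal SAP window.** Share = (end of study day − end of treatment-period day) / end of study day.

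| Case | Days outside | Share |
|---|---|---|
| Nominal, period ends Day 169 | 225 − 169 = 56 (Days 170–225) | 56/225 = 24.9% |
| Period ends Day 172 (SAP Table 1) | 225 − 172 = 53 (Days 173–225) | 53/225 = 23.6% |
| Late Week 24, early Week 32 visit | 220 − 172 = 48 | 48/220 = 21.8% |
| Early Week 24, late Week 32 visit | 230 − 166 = 64 | 64/230 = 27.8% |

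**Closeness to dosing.** There are 1 + 12 = 13 dosing visits, the last on Day 169. Days 170 to 183 are 14 days, so 14/56 = 25% of the excluded days lie within one 2-week dosing interval of an injection.

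**Outputs that can change for completers.** SAP 4.12.2 lists 14 table summaries, 12 of them TEAE-based. Discontinuation and interruption of study drug cannot be affected by an event that starts after a completer's last dose, so 12 − 2 = 10 can change. The overview table has 18 lines, 9 of them TEAE-based; 9 − 2 = 7 can change. The AESI incidence and risk-difference tables in SAP 4.12.3 can change as well.

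**Patients who stop dosing early.** Protocol 3.4 follows them for a further 8 weeks, but the SAP does not say when their treatment period ends. If it ends at the last dose, an event that starts before the next planned dose and leads to discontinuation would drop out of the discontinuation table. For these patients the discontinuation and interruption outputs are therefore not safe. The documents do not support a share of days for them.

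**The date rules.** SAP 4.2 adds: "Where the AE start date is missing, adverse events will be assumed to be treatment-emergent, unless there is clear evidence" that they began before first dose. The partial-date rules in SAP 4.3.2 likewise impute the start date from the first dose date or the AE end date, with no limit at the last dose or Week 24. Under the literal definition, an event with an unknown start date counts, while one with a known follow-up onset does not.

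**The case against.** The strongest reply is that the SAP text is shorthand for the protocol's window.

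- The protocol sentence itself stretches the term treatment period over follow-up, and the SAP is written from that protocol.
- SAP 4.12.7 uses the term loosely, placing Week 28 under both treatment and follow-up.
- No AE date rule in the SAP sets a cut-off at the end of treatment, which fits the protocol's window.

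This reading is plausible, and a truncated copy is a likely explanation. It also means the mismatch with the missing-date rule is a contradiction only if the narrow window is meant. But nothing in the SAP restores the end point, and SAP 3.1, the schedule headings and SAP 4.11.4 all use the term for 24 weeks.

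The second reply is that little is lost. This stands in part. All-AE and serious-AE tables by system organ class and preferred term remain, the overview keeps all-AE lines by maximum severity and relatedness, and every AESI is listed by subject. However, the all-AE outputs also take in events from consent onwards, so they do not replace the TEAE tables. The AESI p-values are unadjusted, and with few patients after termination the 4-subject trigger may not be met in any case.

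Third, the share of days may overstate the share of events. Protocol 8.6 reports that conjunctivitis with another product in the class typically began in Weeks 4 to 8.

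**Conclusion.** SAP 4.2 is wrong as written: it omits an end point that the protocol states, and the SAP's own period definitions then exclude follow-up. For a completer on nominal days, 56 of 225 days (24.9%) fall outside the window, with a range of 21.8% to 27.8% over the allowed visit windows. Up to 10 of 14 AE summaries, 7 of 18 overview lines and the AESI tables are exposed. These figures assume a completer and the literal reading.

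Severity is moderate. Confidence that the narrow window would actually be applied is medium.

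A reader might infer more than the documents support:

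- **That the sponsor chose a narrower safety window.** The text shows an omission; it does not show intent.
- **That about a quarter of events would be lost.** The figures are shares of days. The number of events moved is not in the documents, and every event stays in the all-AE outputs or listings.
- **That a reaction starting the day after the last injection is necessarily excluded.** If the period runs to Day 172, a Day 170 onset still counts.
- **That SAP 4.15 is silent on changes.** It declares several; none concerns the TEAE definition.
- **A loss of chance of reaching the AESI trigger.** This would need arm sizes, incidences and an onset pattern that the documents do not give.

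**What to change.** Restate the SAP 4.2 definition to match protocol 9.6: an AE that starts or worsens at any time from the first administration of study treatment through the end of the follow-up period, related or not. Use that definition for the TEAE flag, the AESI tables and the 4-subject count.

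If a shorter window is intended, declare it in SAP 4.15 as a change from the protocol, with the day on which it ends for completers and the rule for patients who stop dosing early.

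The cost is one sentence and one flag derivation. No new data are needed, because AEs are already collected to Visit 17. Reported TEAE and AESI incidences may rise slightly compared with the literal reading.

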### Treatment Compliance

Treatment compliance (%) will be calculated as:

$$\frac{\text{Total Amount of Study Drug Administered (mL)}}{\text{Total Amount of Study Drug Planned (mL)}} \times 100\%$$

## 4.3 General Presentation Considerations

Continuous data that are assumed to be normally distributed will be summarized in terms of the mean, standard deviation (SD), median, minimum, maximum and number of observations. Continuous data that are expected to be skewed will be presented in terms of the maximum, upper quartile, median, lower quartile, minimum and number of observations. The minimum and maximum will be reported to the same number of decimal places as the raw data recorded in the database. The mean, median, lower quartile and upper quartile will be reported to one more decimal place, and the SD (and the standard error [SE], if applicable) will be reported to two more decimal places, than the raw data recorded in the database. In general, the maximum number of decimal places reported shall be four for any summary statistic.

Categorical data will be summarized in terms of the number of subjects providing data at the relevant time point (n), frequency counts and percentages. Any planned collapsing of categories will be detailed in the SAP text and the data displays.

Percentages will be presented to one decimal place except 100%. 100% will be presented as 100% instead of 100.0%. Percentages will not be presented for zero counts. Percentages will be calculated using the number of subjects (n) as the denominator. If sample sizes are small, the data displays will show the percentages, but any textual report will describe frequencies only. A missing category shall be included only for categorical variables where no data is available. The missing category will be omitted if there were no missing values for that variable.

Changes from baseline in categorical data will be summarized using shift tables where appropriate.

Laboratory values contain ‘ $\geq x$ ’ or ‘ $x \leq$ ’ will be taken as the value of x in the analysis. If a laboratory value contains ‘ $y <$ ’ then y minus 0.001 will be used for the analysis. If a laboratory value contains ‘ $z >$ ’ then z plus 0.001 will be used for the analysis.

P-values greater than or equal to 0.001, in general, will be presented to three decimal places. P-values less than 0.001 will be presented as “ $<0.001$ ”. P-values greater than 0.999 will be presented as “ $>0.999$ ”.

Confidence intervals will be presented to one more decimal place than the raw data.

